Official Title:

Effect of different labor analgesics on maternal UtA, fetal UA and MCA blood flow index observed by Doppler ultrasonography: A prospective randomized double-blinded controlled trial

Document Date:

March 1, 2021

Study protocol

1. Study design

Pregnant women of ASA grade I to II, aged 20 to 35 years, weighing 50 to 100 kg, 150-175 cm in height, and 37 to 41 weeks of gestation were included in the study. Women with contraindications of spinal anesthesia, maternal complications (such as pregnancy-induced hypertension, preeclampsia, cardiovascular and cerebrovascular diseases, etc.), abnormal uterine contractions, abnormal placental function or position, signs of fetal distress, and known fetal malformations were excluded. The patients who were failed to administer combined spinal and epidural block analgesia, those who were transferred from vaginal trial labor to cesarean section, those who could not cooperate with ultrasound detection, and those who needed to use oxytocin were excluded. The study was planned and implemented in accordance with the Declaration of Helsinki.

2. Randomization and blinding

90 parturients in the study were randomly assigned to Sufentanil group (S, n=30), Ropivacaine group (R, n=30) and Sufentanil added to Ropivacaine group (SR, n=30) by non-blind personnel according to the computer random number table, and the allocation was hidden. The solution was prepared by an unblinded anesthesiologist and packaged in a blind way and administered by another anesthesiologist. The patients, anesthesia providers, data recorders, ultrasound examiners, obstetrical staff, and nursing staff remained blinded to group assignment throughout the study.

3. Study intervention

At the time of request for labor analgesia, patients were randomized to receive either sufentanil 5 µg (Group S), ropivacaine 3mg (Group R), or sufentanil 2.5 µg added to ropivacaine 2.5 mg (Group SR) into the subarachnoid space. All groups received the standard epidural solution that contained 0.1% ropivacaine with 0.25 µg/ml sufentanil. Routine obstetric and anaesthetic monitoring was given after maternal entered the delivery room.

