An experienced the anesthesiologist select L3-4 lumbar vertebra clearance to puncture with standard sterile technique using loss of resistance when the puerpera palace has expanded to about 3 cm. After the puncture reached the epidural space, a 25-gauge lumbar anesthesia needle was used to puncture into the subarachnoid space. 2 mL of anesthetic drug as determined by her group randomization were administered into the cavity through the lumbar anesthesia needle after cerebrospinal fluid flow out. A 19-gauge spring-wound catheter was threaded 4-6 cm into the epidural space. All patients received a test dose of 3 ml of 1.5% lidocaine followed by an initial loading dose of 5 ml of the standard epidural solution. Epidural catheters into vessels or subarachnoid space were excluded. An analgesic pump (PCEA pump, 100ml) containing standard epidural solution was then connected to the epidural catheter at a background continuous infusion rate of 5 mL/h. The visual analogue score for pain (VAS) was performed 15 minutes after the injection dose, and if the VAS score fell below 3, the case was included in the study.

An anesthesia provider assessed the adequacy of analgesia for the patients throughout the duration of labor. Any breakthrough pain was managed with a physician-administered epidural bolus. All obstetric analgesia procedures were performed by the same anesthesiologist to reduce errors due to technical reasons.

4. Ultrasonic examination method

The patients were placed in a supine position with calm breathing to perform doppler ultrasonography during the interval of contractions. Ultrasound probe was

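### Randomised women enter the study only if VAS is below 3 after the assigned spinal drug, and no all-randomised analysis set is named, so the between-arm Doppler comparison can be biased

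*Combined protocol and SAP*

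**What the plan says.** The order of events is explicit.

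- **Randomisation.** Section 2: "90 parturients in the study were randomly assigned to Sufentanil group" and two other arms, with 30 in each. Section 3 gives the timing: "At the time of request for labor analgesia, patients were randomized to receive either" one of three intrathecal regimens.
- **Treatment.** Section 3: the assigned drug goes into the subarachnoid space. What follows is common to every arm: "All patients received a test dose of 3 ml of 1.5% lidocaine followed by an initial loading dose of 5 ml". The loading dose is drawn from the same epidural mixture throughout.
- **The check.** Section 3: VAS is scored 15 minutes after the injection dose, and "if the VAS score fell below 3, the case was included in the study".
- **Primary outcomes.** Section 5: S/D, PI and RI of three arteries before analgesia (T0) and at 30, 60 and 90 minutes (T1 to T3).
- **Other removals.** Section 1: "The patients who were failed to administer combined spinal and epidural block analgesia, those who were transferred from vaginal trial labor to cesarean section", and also "those who could not cooperate with ultrasound detection, and those who needed to use oxytocin were excluded". Section 3: "Epidural catheters into vessels or subarachnoid space were excluded".
- **Later boluses.** Section 3: "Any breakthrough pain was managed with a physician-administered epidural bolus". Nothing is said about Doppler values measured afterwards.

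Section 7 names the software, summaries, tests and significance level. It names no analysis set, no rule for missing or replaced women, and no sensitivity analysis. Nowhere is it said whether 30 per arm is counted before or after the VAS check.

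**The concern.** Randomisation makes the arms comparable at the moment of assignment. A filter applied later keeps that comparability only if it works alike in each arm or is unrelated to the outcome. Here the filter is pain relief after the study drug, and the arms differ in exactly that drug. Blinding does not help, because the drug itself can decide who passes.

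If pass rates differ and pain relates to the Doppler indices, the women compared at T1 to T3 are not the groups that were randomised. The comparison can then show a difference that is not a drug effect, or hide part of a real effect that acts through pain relief. VAS is not a listed outcome and no reporting of exclusions by arm is planned, so a reader of the results could not tell whether this had happened.

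**Working it through.** **The plan's own figure.** The only figure is 30 per arm. It cannot be reproduced, because no effect size, SD, power or dropout allowance is given. For scale, by the normal approximation with two-sided alpha 0.05, 30 against 30 has 80% power for a difference of (1.960 + 0.842) × √(2/30) = 0.723 SD.

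**Inputs.** From the documents: 30 per arm, the VAS check before T1, an independent-sample t test, and P < 0.05 (two-sided assumed). Assumed, because the documents are silent: the failure fraction f in each of two arms, and the correlation ρ between 15-minute pain and a Doppler index.

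**Step 1: bias when the drugs do not affect Doppler.** Let pain and the Doppler index be standard normal with correlation ρ, and drop the worst fraction f of an arm. Mean pain among those kept is −λ(f), with λ(f) = φ(z)/(1 − f) and z the (1 − f) quantile.

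- λ(0.05) = 0.1031/0.95 = 0.109
- λ(0.10) = 0.1755/0.90 = 0.195
- λ(0.20) = 0.2800/0.80 = 0.350
- λ(0.30) = 0.3477/0.70 = 0.497

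Bias = ρ × [λ(f₂) − λ(f₁)] in SD units. For 5% against 30% and ρ = 0.5: 0.5 × (0.497 − 0.109) = 0.194.

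**Step 2: type I error.** Noncentral t with noncentrality = bias × √[n₁n₂/(n₁ + n₂)], unit SD and n₁ + n₂ − 2 degrees of freedom. For the same case without replacement, n is 28.5 and 21, so the noncentrality is 0.194 × √(598.5/49.5) = 0.675 and the type I error is 0.101. With replacement to 30 and 30 it is 0.194 × √15 = 0.751, giving 0.115.

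| Failure, two arms | Bias in SD, ρ 0.3 / 0.5 | Type I error, no replacement | Type I error, replaced to 30 |
|---|---|---|---|
| 5% v 5% | 0 / 0 | 0.050 / 0.050 | 0.050 / 0.050 |
| 5% v 10% | 0.026 / 0.043 | 0.051 / 0.053 | 0.051 / 0.053 |
| 5% v 20% | 0.072 / 0.121 | 0.058 / 0.071 | 0.059 / 0.075 |
| 5% v 30% | 0.116 / 0.194 | 0.068 / 0.101 | 0.073 / 0.115 |

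These figures are for one two-arm test of one index at one time. Replacement leaves the bias unchanged and slightly raises the error rate. Simulation with 200,000 runs per case agrees within 0.006. A separate simulation of 20,000 trials at ρ = 0.5 also compared the selected women with all randomised women: 7.0% against 4.8% (5% v 20% failure) and 10.5% against 5.2% (5% v 30%).

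**Step 3: if pain relief itself changes the index.** With a common cut-off, failure of 5% against 10%, 20% or 30% implies mean pain differing by 1.645 − 1.282 = 0.363, 1.645 − 0.842 = 0.803 or 1.645 − 0.524 = 1.120 SD. The check removes ρ × [λ(f₂) − λ(f₁)] from a true difference of ρ times those values. The share lost is 0.0864/0.363 = 23.8%, 0.2414/0.803 = 30.1% and 0.3881/1.120 = 34.6%.

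**Step 4: numbers kept.** If 30 is counted before the check and nobody is replaced, 20% failure leaves 24 in an arm and 30% leaves 21. With 24 or 21 in both arms, power for 0.723 SD falls from 80% to 71% or 65%.

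**The case against.** The strongest reply concerns size. The documents give neither pass rates nor a correlation, and the range used could be too high. At ρ = 0.1, even 5% against 30% failure gives only 0.04 SD and a type I error of 0.052 to 0.053. All arms receive the same lidocaine test dose and epidural solution, which may bring pass rates together. This stands, and it is why the claim is that the comparison can be biased, not that it is. It does not restore the protection of randomisation, and the plan provides no data from which to show that the harmless case occurred.

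The percentages in step 3 are the same absolute shift as in step 1, expressed against an assumed true effect. They also assume that pain at 15 minutes carries through to T1 to T3. Both remarks are right, and the percentages should not be read as a second harm.

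Some of the other removals may be harmless. A puncture that fails before the spinal drug is given cannot depend on that drug. The catheter sentence may mean that misplacement was ruled out, not that women were dropped. That is fair. Caesarean section and oxytocin can arise after treatment, however, and an all-randomised set settles all of these together.

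The natural reading of section 2 is that 30 per arm counts randomised women, and no replacement is described. The inclusion sentence in section 3 leaves doubt, so both counts are shown.

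Finally, the effect under an effective block is a legitimate question. It is, but a comparison restricted to responders is not protected by randomisation and should not be the primary one.

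**Conclusion.** The concern holds, and the plan must be changed. As written, it selects women on a response to the assigned treatment before any post-baseline primary measurement, and no analysis set corrects this. That conclusion rests on the text alone.

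The size rests on assumptions: a normal model, ρ of 0.3 to 0.5, and 5% failure in one arm against 5 to 30% in the other. Across that range the bias runs from 0 to 0.19 SD. The type I error runs from 0.050 to 0.101, or to 0.115 with replacement. At 5% against 10% failure the effect is negligible. In this model, bias needs both unequal failure and a link between pain and the index. If selection worked differently in each arm, equal pass rates alone would not rule it out.

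**What to change.** In the protocol and section 7:

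1. Remove VAS below 3 as a condition for inclusion in the analysis.
2. Define the primary analysis set as all randomised women in their assigned arm.
3. Obtain T1 to T3 Doppler wherever feasible, whatever the 15-minute VAS and despite failed block, misplaced catheter, oxytocin or later caesarean. Count women who cannot be scanned as missing data, by arm.
4. State that Doppler values measured after a breakthrough bolus stay in the primary analysis. Management of breakthrough pain is unchanged.
5. Report by arm the 15-minute VAS, the proportion below 3, the number and timing of boluses, and every randomised woman not analysed, with the reason.
6. Keep the VAS-below-3 subset as a labelled sensitivity analysis.
7. State whether 30 per arm means randomised or included.

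**Cost.** Mostly wording, since VAS is already measured. At 5 to 30% failure in every arm, 0.05 × 90 = 4.5 to 0.30 × 90 = 27 women (about 5 to 27) need three further scans each, plus those now dropped for other reasons. The drawback is that women with incomplete relief, or with a bolus before T1, dilute the contrast under an effective block. The sensitivity analysis still shows that contrast, without the protection of randomisation.

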placed on fetal head area. Middle cerebral arteries (MCA) run anteriorly on both sides of the ring of cerebral arteries at the position of the double head diameter (see Figure 1A). We can get waveforms of MCA examined by pulsed wave doppler (see Figure 1B). The probe was placed at the placenta area, and we can see the fetal umbilical cord connecting to the center of the placenta. Umbilical artery (UA) could be identified by color flow, and its waveforms were examined by pulsed wave doppler (see Figure 1C and 1D). The probe was placed at the midpoint of the groin. The right and left uterine arteries (UtA) could be identified by color flow at the apparent crossover with the external iliac arteries, and pulsed wave doppler was used to obtain waveforms (see Figure 1E and 1F). 3 to 10 arterial spectrograms with clear edges and no background noise at baseline were selected. The above arterial blood flow indexes were measured three times and the average value was taken. The S/D、PI、RI value of MCA、UA、UtA can be measured automatically by ultrasound instrument. All doppler examinations were performed by the same sonographer.

5. Primary outcomes

The main indexes were doppler blood flow indexes (S/D, PI, RI value) of UtA, UA, MCA before analgesia (T_0) and 30 min (T_1), 60min (T_2), 90 min (T_3) after analgesia in the three groups.

6. Secondary outcomes

Fetal heart rate (FHR) and mean artery pressure (MAP) at T_0 , T_1 , T_2 and T_3 , neonatal weight, time of each stage of labor, rate of midwifery, neonatal umbilical artery blood gas index and Apgar score at 1 min, 5 min, 10 min after birth of the three groups were included in the secondary indicators.

7. Statistical Analysis Plan

In this study, SPSS 13.0 was used for statistical analysis, and GraphPad Prism 8 was used for mapping. Measurement data were expressed as mean \pm standard deviation ($\bar{x}\pm s$), and categorical data were expressed as frequency, percentage, or rate. Paired t

test was used for intra-group comparison and independent sample t test was used for inter-group comparison of measurement data conforming to normal distribution. The measurement data with non-normal distribution were analyzed by rank sum test. Chi-square test was used for statistical analysis of categorical data. $P < 0.05$ indicates statistical significance.

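### Nine unranked primary Doppler indexes, compared pairwise across three arms at three times, give 81 unadjusted tests and about 4 expected false positives if the arms do not differ

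*Combined protocol and SAP*

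**What the plan says.** Section 5 (Primary outcomes) states: "The main indexes were doppler blood flow indexes (S/D, PI, RI value) of UtA, UA, MCA before analgesia". It continues through the post-analgesia times, ending with "60min (T_2), 90 min (T_3) after analgesia in the three groups". That makes three indexes in each of three vessels, at baseline (T0) and three later times, all primary and none given priority. Section 2 allocates 90 women to three arms of 30.

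For between-group comparisons, section 7 (Statistical Analysis Plan) states: "independent sample t test was used for inter-group comparison of measurement data conforming to normal distribution". For other measurement data: "The measurement data with non-normal distribution were analyzed by rank sum test". It does not say whether this means a two-group or a three-group rank test. The only decision rule is that P < 0.05 "indicates statistical significance". Sections 5 and 7 contain no hierarchy, no global test for normally distributed data, no repeated-measures model and no adjustment for multiple testing.

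**The concern.** A two-sample t test compares two arms, so three arms need three tests for every index at every time. With nine unranked indexes and three post-analgesia times, the plan creates many separate routes to a positive primary result, each open at the 5% level. The 5% threshold then does not give a 5% error rate for the primary conclusion.

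At stake is the trial's main claim. One significant vessel, index, time or pair could be reported as a drug effect on uteroplacental or fetal blood flow, and a reader could not distinguish it from chance. Because the indexes are correlated, false positives tend to arrive together, so several agreeing results from one chance imbalance could look like corroboration.

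**Working it through.** The documents give no test count, sample-size calculation or family-wise error rate, so there is no stated figure to reproduce.

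**1. Inputs.** Indexes: 3 (S/D, PI, RI) x 3 vessels (UtA, UA, MCA) = 9 (section 5). Post-analgesia times: 3 (section 5). Arms: 3 of 30 (section 2), hence 3 pairs. Level: 0.05 per test (section 7), assumed two-sided. One UtA value per woman is assumed; section 4 images both sides but does not say how they are combined.

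**2. Test count.** 9 x 3 x 3 = 81. This leaves out T0 (with it, 9 x 4 x 3 = 108 tests, 108 x 0.05 = 5.4 expected), the within-group paired tests (81 more) and all secondary outcomes.

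**3. Expected false positives if the arms do not differ.** 81 x 0.05 = 4.05. Expectations add, so correlation does not change this figure.

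**4. Chance of at least one.** Independence would give 1 - 0.95^81 = 98.4%, but the tests are not independent, so that figure is not used. Null trials were simulated instead: 3 arms x 30, 4,000 replicates per scenario, log-normal S/D, normal PI, and RI set to 1 - 1/(S/D). The last setting assumes RI = (S - D)/S, which the documents do not define. All correlations are assumed.

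| PI with S/D | Between vessels | Between times | Chance of at least one P < 0.05 in 81 |
|---|---|---|---|
| 0.6 | 0 | 0.3 | 0.887 |
| 0.6 | 0.1 | 0.4 | 0.877 |
| 0.7 | 0.2 | 0.5 | 0.832 |
| 0.8 | 0.3 | 0.6 | 0.786 |
| 0.9 | 0.3 | 0.7 | 0.717 |
| 0.9 | 0.4 | 0.8 | 0.657 |
| 0.95 | 0.5 | 0.8 | 0.621 |
| 0.95 | 0.5 | 0.9 | 0.544 |

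The mean number of false positives was 3.94-4.14, in line with 4.05.

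**5. Sensitivity.**
- RI dropped: 6 x 3 x 3 = 54 tests, 54 x 0.05 = 2.7 expected; chance of at least one 0.863 down to 0.514.
- Most favourable reading, with every index non-normal and the rank sum test meaning Kruskal-Wallis: 9 x 3 = 27 tests, 27 x 0.05 = 1.35 expected; chance of at least one 0.538 down to 0.273.
- One index at one time, three pairwise t tests: 0.124 simulated (40,000 replicates); independence would give 1 - 0.95^3 = 0.143.

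**6. Error rate of the replacement.** Analysis of covariance on the T1-T3 mean adjusted for T0, 6,000 replicates, vessel correlation 0, 0.3 or 0.5 and time correlation 0.4, 0.6 or 0.8.

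| Procedure | Arms equal | One arm shifted 2 SD |
|---|---|---|
| One endpoint: global test at 0.05, then pairs at 0.05 | 0.044-0.050 | 0.048-0.050 |
| PI in three vessels: global test and pairs each at 0.05/3 | 0.043-0.049 | 0.045-0.049 |
| Holm across the vessels' global tests, then pairs at 0.05 | not reported | 0.124-0.142 |

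**7. Power of the replacement.** With 30 analysed per arm and 90 - 4 = 86 df, a pairwise difference of d adjusted SDs has noncentrality d x sqrt(30/2) = 3.873d. Power of 80% needs d = 0.732 at level 0.05 and d = 0.850 at 0.05/3. If the global test must be significant first and the third arm lies midway (20,000 replicates), power at level 0.05 is 0.778 at 0.80 SD and 0.832 at 0.85 SD; at 0.05/3 it is 0.806 at 0.95 SD.

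**The case against.** The best reply is that 81 is inferred: the plan never lists the pairs, and the rank sum test could be a three-group test. This is a fair condition on the count. But the t test is named for normally distributed data and no pair is excluded, and even the 27-test reading leaves a 27-54% chance of a false positive.

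A mean of 4 can also mislead, because false positives cluster. In rerun scenarios the median was 3 under weak and middle correlation and 1 under the strongest, where about 45% of null trials had none. That stands as a caution on reading the mean, and it is why the chance of at least one is given beside it. Nor is 50-90% a bound: other assumed patterns, including uncorrelated endpoints, gave 66-97%.

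The relation between RI and S/D is an assumption, and it need not hold exactly if each index is averaged separately over the three measurements. If it does hold, rank tests of the two coincide, so the 27 contain only 18 distinct tests (18 x 0.05 = 0.9 expected). The conclusion does not rest on RI.

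Finally, the trial could be read as a descriptive Doppler panel with no single success rule. The documents do not say so: the title calls it a randomized double-blinded controlled trial and section 5 calls these outcomes primary. If description is the aim, the plan should state it and label the results exploratory.

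**Conclusion.** The concern holds and must be fixed. Following sections 5 and 7 as written gives 81 unadjusted primary comparisons, with 4.05 false positives expected if the arms do not differ. The count assumes that all three pairs are tested at each post-analgesia time and that each woman has one UtA value. The 4.05 needs no assumption about correlation, only that each test has its nominal 5% level. The roughly 50-90% chance of at least one false positive does depend on correlations that the documents do not supply. On no reading examined is the family-wise error near 5%.

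**What to change.** Name one primary endpoint. UtA PI averaged over T1-T3 and adjusted for T0 is an example; the choice of vessel and index belongs to the investigators. State how right and left UtA are combined and how a woman with a missing reading enters the average. Test the three arms with one global 2-df test at 0.05 and run the three pairwise contrasts at 0.05 only if it is significant. With three arms this holds the family-wise error at 5%.

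If all three vessels must stay primary, use PI only, and test each vessel's global test and its pairwise contrasts at 0.05/3. Do not apply Holm across vessels and then test pairs at 0.05: with one arm shifted, that falsely separates the two equal arms in 12-14% of trials.

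Make S/D, RI, the separate time points and the within-group paired tests secondary or descriptive. The plan is in the past tense, which may be only a matter of style. If outcome data had been seen when the endpoint was chosen, say so and label the results exploratory.

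**Cost.** This is a SAP text change with no new data collection, but most nominal P < 0.05 results become supportive only. Averaging over T1-T3 could dilute an effect confined to 30 minutes. Power is limited: with the global test required first and the third arm midway, about 0.8 SD is detectable with 80% power for one endpoint and about 0.95 SD for three vessels. The documents give no sample-size calculation against which to judge whether such differences are plausible.

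### T0 measurements and neonatal weight are listed as outcomes and fall under the general between-arm test rule, but no positive among those tests could show a drug effect

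*Combined protocol and SAP*

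**What the plan says.** Section 5 (Primary outcomes) reads "The main indexes were doppler blood flow indexes (S/D, PI, RI value) of UtA, UA, MCA before analgesia (T_0" and goes on to the three post-analgesia times, T1 to T3, in the three groups. T0 is thus one of four time points in the primary outcome.

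Section 6 (Secondary outcomes) opens with "Fetal heart rate (FHR) and mean artery pressure (MAP) at T_0 , T_1 , T_2 and T_3 , neonatal weight" and closes by saying that these, with the other items, "of the three groups were included in the secondary indicators".

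Section 7 (Statistical Analysis Plan) has one between-arm rule for normally distributed continuous data: "independent sample t test was used for inter-group comparison of measurement data conforming to normal distribution". A rank sum test replaces it for non-normal data, and significance is set at P below 0.05. The section exempts no time point or variable, gives T0 no covariate role and states no adjustment for multiple tests.

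Section 2 gives the design: "randomly assigned to Sufentanil group (S, n=30), Ropivacaine group (R, n=30) and Sufentanil added to Ropivacaine group (SR, n=30".

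**The concern.** An outcome should be something the treatment could alter. T0 is measured before the spinal injection. Birth weight is recorded afterwards, but it is in effect fixed by the time a spinal dose is given at about 3 cm dilation (section 3). A between-arm test on either cannot answer the trial's question, whatever its result.

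The risk is in interpretation. A significant T0 or weight difference could be taken for a finding or for failed randomisation. A non-significant one, with 30 women per arm, could be taken as evidence of balance. Neither inference is sound, and either could colour the reading of the T1 to T3 results. The documents do not say how T0 results will be interpreted, so this is a risk and not a stated intention.

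**Working it through.** The plan states no test count, so there is no figure of its own to reproduce.

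**Inputs from the documents**
- Doppler variables at T0 (section 5): 3 indexes x 3 vessels = 9.
- Secondary variables of the same kind (section 6): FHR at T0, MAP at T0 and neonatal weight = 3.
- Arms (section 2): 3 arms of 30, so 3 pairs.
- Significance level (section 7): 0.05 per test. Sidedness is not stated; two-sided is assumed.

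**Count, with every pair tested**
- Tests the drug cannot influence: (9 + 2 + 1) x 3 = 36, of which 9 x 3 = 27 are primary and 3 x 3 = 9 secondary.
- All primary between-arm tests: 9 x 4 times x 3 pairs = 108, so 27/108 = one quarter are at T0.
- Expected false positives with no real difference: 36 x 0.05 = 1.8, of which 27 x 0.05 = 1.35 are primary. Correlation between tests does not change these expectations.

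**Chance of at least one false positive**
- If all tests were independent: 1 - 0.95^36 = 0.84 for the 36, and 1 - 0.95^27 = 0.75 for the 27.
- They are not independent, because pairs share arms and S/D, PI and RI of one vessel move together. The documents give no correlations, so a range was assumed. The table is from 20,000 simulated trials per row, with 3 arms of 30, normal data, two-sided t tests, and vessels, FHR, MAP and weight mutually independent.

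| Assumed within-vessel correlation | Mean false positives (36 tests) | At least one of 36 | At least one of 27 |
|---|---|---|---|
| 0 | 1.81 | 0.79 | 0.69 |
| 0.5 | 1.80 | 0.75 | 0.63 |
| 0.9 | 1.84 | 0.65 | 0.49 |
| 0.97 | 1.77 | 0.60 | 0.40 |

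Adding a between-vessel correlation of 0.2 to the 0.9 case gives 0.64 for the 36 tests.

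**Sensitivity of the count**
- Right and left UtA analysed separately: 12 Doppler variables, (12 + 2 + 1) x 3 = 45 tests, and 45 x 0.05 = 2.25 expected.
- One comparison per variable: 12 tests, and 12 x 0.05 = 0.6 expected.

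**Could a T0 difference be systematic?** Women are randomised at the request for analgesia (section 3). They are kept only if VAS falls below 3 at 15 minutes after the injection (section 3), and those who go to cesarean section or need oxytocin are excluded (section 1). These events can follow the drug and can differ by arm. As an illustration, suppose one arm loses a fraction q on VAS, another loses none, and VAS correlates r with a T0 variable. With z the standard normal (1 - q) quantile and phi the normal density, the retained means differ by r x phi(z)/(1 - q) SD.
- q = 0.1, r = 0.2: 0.04 SD.
- q = 0.3, r = 0.4: 0.4 x 0.348/0.7 = 0.20 SD.

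With 30 retained per arm the standard error is sqrt(2/30) = 0.258 SD, and the rejection rate per test is about 5% and 12% respectively. Both q and r are assumptions; the documents give neither.

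**The case against.** A reader might go further and infer that these null hypotheses are true by design, so that any P below 0.05 can only be chance. The documents do not support that. It would hold if the randomised groups were analysed intact, but women are dropped on events that can follow the drug. A T0 or weight difference among those retained may therefore reflect selection. Nor should an imbalance be dismissed in advance as noise. It still would not be a drug effect on that variable, and a P value cannot separate chance from selection.

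It may also be objected that section 5 is only a measurement schedule, and that nothing says T0, or every pair, is tested between arms. It is true that neither is stated in words. The inference is reasonable because T0 stands inside the primary outcome, the rule covers measurement data without exception, and a two-sample test is the only stated between-arm method for normal data in a three-arm trial.

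T0 has a proper use as the natural reference for the within-arm paired tests in section 7. This stands and limits the remedy. Sections 5 and 6 are the only places that define T0, so striking it from them without a replacement would remove the pre-analgesia measurement from the plan.

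Finally, the gain is limited: 108 - 27 = 81 unadjusted primary tests would remain. That is a separate problem and does not justify keeping tests that cannot inform the trial's question.

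**Conclusion.** The point holds in this form. T0 Doppler values, T0 FHR and MAP, and neonatal weight are classed as outcomes, and nothing exempts them from between-arm testing. Under pairwise testing this gives 36 tests and 1.8 expected false positives if there is no selection. These two figures rest only on the listed variables, the three arms, the 0.05 level and the pairwise reading. The chance of at least one false positive, roughly 60-75%, also rests on assumed within-vessel correlations of 0.97 down to 0.5.

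A positive would show chance or post-randomisation exclusion, not a drug effect; the documents do not support saying that it must be chance. The defect does not invalidate the T1 to T3 comparisons. It should be corrected because a quarter of the primary between-arm tests cannot bear on the trial's question and the correction costs almost nothing.

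**What to change.** - Sections 5 and 6: define the Doppler, FHR and MAP outcomes at T1, T2 and T3 only.
- In the same sections, keep T0 explicitly as the pre-analgesia baseline measurement and name it as the reference for within-arm change.
- Section 7: preferably prespecify T0 as a covariate in the between-arm comparison of T1 to T3, for example by analysis of covariance or a mixed model.
- Section 6: move neonatal weight to the table of descriptive characteristics.
- Section 7: state that T0 values and neonatal weight are summarised by arm without between-arm P values.
- Report the number of and reason for post-randomisation exclusions by arm, so that any imbalance in T0 or weight can be interpreted.

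The cost is wording and slightly fewer P values: primary between-arm tests fall from 108 to 81, and all 36 uninformative tests go. The covariate step also replaces a t test with a regression model. No new patients or measurements are needed.
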